## QT prolonging medication

The following drugs are generally recognized to have an association with QT prolongation. This list is not considered to be all inclusive and any questions regarding the QT prolongation potential should be discussed with the Novartis Medical Monitor.

Drugs that are generally accepted by the QTdrugs.org Advisory Board of the Arizona CERT to have a risk of causing torsade de pointes are listed below.

Generic Name	Brand Name	Class
Bepidil	Vascor ®	Anti-anginal / heart pain
Amiodarone	Cordarone ®	Anti-arrhythmic / abnormal heart rhythm
Amiodarone	Pacerone ®	Anti-arrhythmic / abnormal heart rhythm
Disopyramide	Norpace ®	Anti-arrhythmic / abnormal heart rhythm
Dofetilide	Tikosyn ®	Anti-arrhythmic / abnormal heart rhythm
Ibutilide	Corvert ®	Anti-arrhythmic / abnormal heart rhythm
Procainamide	Pronestyl ®	Anti-arrhythmic / abnormal heart rhythm
Procainamide	Procan ®	Anti-arrhythmic / abnormal heart rhythm
Quinidine	Cardioquin ®	Anti-arrhythmic / abnormal heart rhythm
Quinidine	Quinaglute ®	Anti-arrhythmic / abnormal heart rhythm
Sotalol	Betapace ®	Anti-arrhythmic / abnormal heart rhythm
Clarithromycin	Biaxin ®	Antibiotic / bacterial infection
Sparfloxacin	Zagam ®	Antibiotic / bacterial infection
Erythromycin	Erythrocin ®	Antibiotic;GI stimulant / bacterial infection; increase GI motility
Erythromycin	E.E.S. ®	Antibiotic;GI stimulant / bacterial infection; increase GI motility
Arsenic trioxide	Trisenox ®	Anti-cancer / Leukemia
Astemizole	Hismanal ®	Antihistamine / Allergic rhinitis
Terfenadine	Seldane ®	Antihistamine / Allergic rhinitis
Pentamidine	Pentam ®	Anti-infective / pneumocystis pneumonia
Pentamidine	NebuPent ®	Anti-infective / pneumocystis pneumonia
Probucol	Lorelco ®	Antilipemic / Hypercholesterolemia
Chloroquine	Aralen ®	Anti-malarial / malaria infection
Halofantrine	Halfan ®	Anti-malarial / malaria infection
Domperidone	Motilium ®	Anti-nausea / nausea
Mesoridazine	Serentil ®	Anti-psychotic / schizophrenia
Thioridazine	Mellaril ®	Anti-psychotic / schizophrenia
Haloperidol	Haldol ®	Anti-psychotic / schizophrenia, agitation
Pimozide	Orap ®	Anti-psychotic / Tourette's tics
Chlorpromazine	Thorazine ®	Anti-psychotic/ Anti-emetic / schizophrenia/ nausea
Cisapride	Propulsid ®	GI stimulant / heartburn
Levomethadyl	Orlaam ®	Opiate agonist / pain control, narcotic dependence
Methadone	Dolophine ®	Opiate agonist / pain control, narcotic dependence
Methadone	Methadose ®	Opiate agonist / pain control, narcotic dependence
Droperidol	Inapsine ®	Sedative;Anti-nausea / anesthesia adjunct, nausea

## 12.4 Appendix 4 SOM230 LFT Management Algorithm (s.c. and LAR Studies)

### Revised SOM230 Abnormal liver function discontinuation criteria:

Hepatic-related discontinuation criteria for all ongoing studies
Study medication should be discontinued immediately if any of the discontinuation criteria below are met:

 
ALT or AST > 3x ULN and Total Bilirubin ≥ 2x ULN and ALP < 2x ULN
 
ALT or AST > 5x ULN and ≤ 8x ULN persistent for more than 2 weeks
 
ALT or AST > 8x ULN
 

Re-challenge of study medication is prohibited once discontinuation criteria are met.

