### 5.2.1 Inclusion criteria

Male or female Age  $\geq$  18 years.

Diagnosis of PLD associated with ADPKD (meeting the Modified Ravine's criteria) or isolated ADPLD (defined by the criteria described by Reynolds et al).

Severe PLD defined as a liver volume  $>4000$ mL or symptomatic disease due to mass effects from hepatic cysts (must be able to undergo MRI or CT scan to determine this).

Not a candidate for or declining surgical intervention.

Capable of providing informed consent.

Life expectancy  $\geq 12$  weeks

Patients with a known history of impaired fasting blood glucose (glucose  $>100$  and  $<126$ ) may be included at the discretion of the PI. These patients should be monitored closely throughout the trial and anti-hyperglycemic treatment adjusted as necessary. Patients that are deemed non eligible due to elevated glucose can be re-screened after adequate medical treatment.

Adequate end organ function as defined by:

Adequate bone marrow function:

- WBC  $\geq 2.5 \times 10^9$ /L
- Absolute Neutrophil Count (ANC)  $\geq 1.5 \times 10^9$ /L
- Platelets  $\geq 100 \times 10^9$ /L
- Hb  $\geq 9$  g/dL

No evidence of significant liver disease:

- Serum bilirubin  $\leq 1.5 \times$  ULN
- INR  $< 1.3$
- ALT and AST  $\leq 2 \times$  ULN

Estimated glomerular filtration rate (eGFR)  $>30$  ml/min/m^2

Serum amylase and lipase  $\leq 1.5 \times$  ULN

Alkaline phosphatase  $\leq 2.5 \times$  ULN

Written informed consent obtained prior to any screening procedures

Willingness and ability to comply with scheduled visits, treatment plans, laboratory tests and other study procedures

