## 6.8 Study drug discontinuation

Study drug must be discontinued and the subject withdrawn from the trial if the investigator determines that continuing would result in significant safety risk for that subject. The following circumstances require study drug discontinuation:

Pregnancy

The occurrence of an adverse event or of a clinically significant laboratory change or abnormality that, in the judgment of the investigator, warrants discontinuation of treatment.

Subjects who have fasting plasma glucose > 240 mg/dL confirmed by repeat measurement

Any CTC grade 3 or higher abnormalities in hematology or chemistry parameters judged clinically significant by the Investigator

Any confirmed QTcF > 500 ms or confirmed increase of QTcF > 60 ms from baseline

ALT or AST > 3x ULN and Total Bilirubin  $\geq$  2 x ULN and ALP > 2 x ULN

ALT or AST > 5x ULN and  $\leq$  8 x ULN persistent for more than 2 weeks

ALT or AST > 8 x ULN

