#### **7.5.4.1 Abnormal liver function management:**

Perform within 72 hours of awareness of abnormal LFTs:

Perform liver-directed medical history and physical examination (i.e. assess occupational hazards, concomitant medications including OTC meds, intercurrent illness, etc)

Liver chemistry tests: ALT, AST, total bilirubin, (fractionate to direct/indirect bilirubin if total bilirubin is > 2.0x ULN), Alb, PT (INR), ALP, and GGT

Perform hepatitis screen: anti-HAV, IgM (to confirm acute hepatitis A), HbsAg, Anti-HBc, anti-HCV (if positive PCR viral load should be assessed), Anti-HEV, ANA antibodies, anti-smooth muscle anti-bodies, CMV, EBV

Perform abdominal ultrasound (liver and biliary tree)

Liver chemistry tests should be monitored every 3-4 days for LAR studies until resolution or return to baseline status.

For ALT or AST > 5x ULN and ≤ 8x ULN:

- Study medication should be temporarily interrupted and liver chemistry tests monitored **every 3-4 days** until resolution or return to baseline
- If resolution or return to baseline does not occur after 2 weeks, the patient should be discontinued.
- If ALT or AST returns to less than 5x ULN, study drug can be resumed and patient can continue study per protocol
- If ALT or AST rises above 5x ULN anytime after study drug is resumed, then study drug should be discontinued immediately.

Resolution return to baseline does not occur after two weeks the patient should be discontinued

If ALT or AST rises about 5X ULN anytime after study drugs resumed and study drug to be discontinued immediately

Study medication should be discontinued immediately if any of the discontinuation criteria below are met: (see appendix 4)

ALT or AST > 3x ULN and Total Bilirubin ≥ 2x ULN and ALP < 2x ULN

ALT or AST > 5x ULN and ≤ 8x ULN persistent for more than 2 weeks

ALT or AST > 8x ULN

Re-challenge of study medication is prohibited once discontinuation criteria are met.

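### Entry allows ALP up to 2.5x ULN, but the combined liver stop turns on ALP at 2x ULN with opposite signs in different sections, so eligible patients with ALP of 2.0-2.5x ULN have no consistent rule

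*Combined protocol and SAP*

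**What the plan says.** Four places in the combined protocol and SAP bear on this.

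- **Section 5.2.1 (inclusion)** sets the entry limit: "Alkaline phosphatase $\leq 2.5 \times$ ULN". It also limits ALT and AST to 2x ULN and bilirubin to 1.5x ULN. The exclusion list in section 5.2.2 gives no tighter ALP limit.
- **Section 7.5.4.1** gives the combined stop as "ALT or AST > 3x ULN and Total Bilirubin ≥ 2x ULN and ALP < 2x ULN".
- **Appendix 4 (section 12.4)** repeats it with the same sign: ALT or AST above "3x ULN and Total Bilirubin ≥ 2x ULN and ALP" below 2x ULN. Any one listed criterion is enough: "Study medication should be discontinued immediately if any of the discontinuation criteria below are met". The other two criteria use ALT or AST alone: above 5x and up to "8x ULN persistent for more than 2 weeks", and above 8x ULN. Both sections prohibit re-challenge once a criterion is met.
- **Section 6.8** lists circumstances that require stopping study drug. It has the same ALT/AST and bilirubin terms, but its ALP term points the other way: "2 x ULN and ALP > 2 x ULN".

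None of these places says how the ALP term applies to a patient whose ALP was already at or above 2x ULN before the first dose.

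**The concern.** A stopping rule built on several laboratory values should have entry limits and triggers that fit together, so that an untreated eligible patient sits on the untriggered side of each term and any term can change during treatment. ALT/AST and bilirubin fit in this way. ALP does not: the 2x ULN cut lies inside the range that the entry criteria allow. For patients who enter at 2.0-2.5x ULN, the ALP term is decided by a pre-treatment value, and which way it is decided depends on which section the site reads.

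At stake is whether a mandatory liver-safety stop applies consistently to every patient the trial admits, in a population selected for liver disease. There is also a practical risk. If only the direction of the sign is corrected, the mismatch with the entry limit will remain.

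**Working it through.** No sample-size, power or alpha figure is involved, and the plan states no figure to reproduce. The check compares thresholds and then evaluates the rule as a logical condition.

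**Step 1. Entry limit against trigger (multiples of ULN).**

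| Test | Entry limit (5.2.1) | Trigger in combined stop | Overlap |
|---|---|---|---|
| ALT/AST | 2 | above 3 | none |
| Total bilirubin | 1.5 | 2 or more | none |
| ALP | 2.5 | below 2 (7.5.4.1, Appendix 4); above 2 (6.8) | 2.0 to 2.5 |

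**Step 2. The combined stop as a condition.** The three terms are joined by *and*:

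- Version A (7.5.4.1, Appendix 4): ALT > 3, bilirubin ≥ 2, ALP < 2.
- Version B (6.8): ALT > 3, bilirubin ≥ 2, ALP > 2.

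Each was evaluated for ALT at 3.01, 4, 5, 6, 8 and 9x ULN and bilirubin at 2, 3, 5 and 10x ULN. That gives 6 × 4 = 24 pairs, all of which satisfy the first two terms, so only ALP can change the result.

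| ALP (x ULN), all eligible | Version A fires | Version B fires |
|---|---|---|
| 0.5, 1, 1.5, 1.99 | 24/24 | 0/24 |
| 2.0 | 0/24 | 0/24 |
| 2.01, 2.25, 2.5 | 0/24 | 24/24 |

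**Step 3. One patient read through each section.** Take ALT 4x, bilirubin 2.5x and ALP 2.2x ULN on treatment.

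- Appendix 4, combined criterion: 4 > 3 true; 2.5 ≥ 2 true; 2.2 < 2 false. Not met.
- Appendix 4, ALT/AST-only criteria: 4 is not above 5 and not above 8. Not met.
- Section 6.8: 4 > 3 true; 2.5 ≥ 2 true; 2.2 > 2 true. Discontinuation required.

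**Step 4. What each way of settling the sign would leave.**

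- *Settled as below 2x ULN.* While ALP stays at 2.0-2.5x ULN, the combined stop cannot fire. The ALT/AST-only stops take over above 8x ULN, and above 5x to 8x ULN once that has lasted more than two weeks. What remains is ALT/AST above 3x to 5x ULN, or above 5x to 8x ULN for up to two weeks, with bilirubin at least 2x ULN.
- *Settled as above 2x ULN.* The combined stop works for patients above 2x ULN, but their ALP term was already true at entry. For them the rule reduces to its ALT/AST and bilirubin terms. A patient at exactly 2.0x ULN is still not covered.

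**The case against.** The strongest reply is that the affected patients do have a combined stop today. A reader might infer from Appendix 4 alone that the rule is switched off for them before the first dose, and that a patient with ALP 2.2x ULN drops to the Table 7 dose rules while an otherwise identical patient at 1.9x ULN must stop. The documents do not support that. As written, the 1.9x patient stops under section 7.5.4.1 and Appendix 4, and the 2.2x patient stops under section 6.8. The fallback to Table 7 would arise only if the sign were settled as below 2x ULN and section 6.8 changed to match.

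Three further parts of the reply stand:

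- The rule uses current values. If ALP falls below 2x ULN during treatment, the Appendix 4 version becomes active. ALP is in the metabolic panel and is monitored every 3-4 days once liver tests are abnormal, so the term is not fixed for the whole trial.
- Other safeguards remain: the two ALT/AST-only stops, the Table 7 bilirubin and transaminase rules (including omission of the dose at bilirubin 2-3x baseline and interruption at ALT/AST above 5x to 8x ULN), the work-up within 72 hours, and investigator judgement under section 6.8.
- The liver-monitoring text placed before section 1.5.2.2 refers to revised liver-test exclusion criteria in a table that is not visible in the text available. A tighter ALP limit there cannot be ruled out, although section 5.2 shows none.

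It can also be said that this is only the sign conflict over again. The same passages do need editing, but correcting the sign does not deal with the entry limit: under one sign the term is already false at entry for patients at 2.0-2.5x ULN, and under the other it is already true for those above 2.0x ULN.

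**Conclusion.** The point holds in a limited form. For eligible patients with ALP above 2x ULN, sections 6.8 and 7.5.4.1 and Appendix 4 give conflicting instructions on the combined stop. At exactly 2.0x ULN neither version applies. Settling the sign as below 2x ULN would leave the combined stop unable to fire while ALP stays at 2.0-2.5x ULN, with the transaminase and bilirubin gap set out above. Settling it as above 2x ULN leaves no such gap for patients above 2x ULN, only an ALP term that their entry value already satisfies.

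The number of patients affected cannot be computed. The documents give no baseline ALP distribution and no rate at which raised transaminases and raised bilirubin occur together. A reader might apply an assumed share to the 48 planned patients, but that would count patients who enter with raised ALP. Only those who also reach ALT/AST above 3x ULN and bilirubin at least 2x ULN together would be affected, which cannot be a larger number.

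The conclusion rests on a literal reading of the thresholds and on section 5.2 as the operative entry list. It takes no position on which sign or which ALP limit is clinically right. That the below-2x wording appears in two places and the above-2x wording in one does not settle the question.

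**What to change.** When the combined stop in sections 6.8 and 7.5.4.1 and Appendix 4 is reconciled to one wording, reconcile it in the same step with the ALP entry limit in section 5.2.1. State explicitly how the ALP term applies to a patient whose baseline ALP is at or above 2x ULN, including a value of exactly 2.0x ULN. The choice of sign, threshold and handling of raised baseline values is for the investigator and sponsor.

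The cost is protocol wording, with the amendment review that section 9 requires for changes affecting subject safety. Baseline ALP is already measured in the screening metabolic panel, so no new test, visit or data item is needed. The sample size and efficacy analysis do not change.

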## 13 Procedures and instructions

### 13.1.1 Publication of results

Any formal presentation or publication of data from this trial may be published after review and comment by Novartis and prior to any outside submission. Novartis must receive copies of any intended communication in advance of publication (at least fifteen working days for presentational materials and abstracts and thirty working days for manuscripts). These requirements acknowledge Novartis' responsibility to provide peer input regarding the scientific content and conclusions of such publications or presentations. Principal Investigation/Institution shall have the final authority to determine the scope and content of its publications, provided such authority

shall be exercised with reasonable regard for the interests of Novartis and, in accord with the trial contract and shall not permit disclosure of Novartis confidential or proprietary information.

### **13.1.3 Discontinuation of study**

Novartis reserves the right to discontinue any study under the conditions specified in the clinical trial agreement.

## **13.2 Ethics and Good Clinical Practice**

This study must be carried out in compliance with the protocol and the principles of Good Clinical Practice, as described in Novartis standard operating procedures and:

ICH Harmonized Tripartite Guidelines for Good Clinical Practice 1996. Directive 91/507/EEC, The Rules Governing Medicinal Products in the European Community.

US 21 Code of Federal Regulations dealing with clinical studies (including parts 50 and 56 concerning informed consent and IRB regulations).

Declaration of Helsinki and amendments, concerning medical research in humans (Recommendations Guiding Physicians in Biomedical Research Involving Human Subjects).

The investigator agrees to adhere to the instructions and procedures described in it and thereby to adhere to the principles of Good Clinical Practice that it conforms to.

### **13.2.1 Institutional Review Board/Independent Ethics Committee**

Before implementing this study, the protocol, the proposed informed consent form and other information to subjects, must be reviewed by a properly constituted Institutional Review Board / Independent Ethics Committee / Research Ethics Board (IRB / IEC / REB). A signed and dated statement that the protocol and informed consent have been approved by the IRB/IEC/REB must be given to Novartis before study initiation. Any amendments to the protocol, other than administrative ones, must be reviewed by Novartis approved by this committee.

### **13.2.2 Informed consent**

We will explain to each subject (or legally authorized representative) the nature of the study, its purpose, the procedures involved, the expected duration, the potential risks and benefits involved and any discomfort it may entail. Each subject must be informed that participation in the study is voluntary and that he/she may withdraw from the study at any time and that withdrawal of consent will not affect his/her subsequent medical treatment or relationship with the treating physician.

This informed consent should be given by means of a standard written statement, written in non-technical language. The subject should read and consider the statement before signing and dating it, and should be given a copy of the signed document. If the subject cannot read or sign

the documents, oral presentation may be made or signature given by the subject's legally appointed representative, if witnessed by a person not involved in the study, mentioning that the patient could not read or sign the documents. No patient can enter the study before his/her informed consent has been obtained.

### **13.2.3 Declaration of Helsinki**

We will conduct the trial in accordance with the principles of the Declaration of Helsinki. Copies of the Declaration of Helsinki and amendments will be provided upon request or can be accessed via the website of the World Medical Association at [http://www.wma.net/e/policy/17-c\\_e.html](http://www.wma.net/e/policy/17-c_e.html).
